Title: Prevention of Post Herpetic Neuralgia by Ultrasound Guided Single Nerve Block in the Emergency Department

NCT: 04530162

Date: August 31, 2021

Prevention of Post Herpetic Neuralgia by Ultrasound Guided Single Nerve Block in the Emergency Department

I. Introduction

Herpes zoster causes significant morbidity on over 1 million Americans every year.^[1] Although the majority of herpes zoster pain will self-resolve within one week, a significant proportion of patients will develop postherpetic neuralgia (PHN), which is characterized by debilitating pain that persists more than three months after the initial symptoms.^[2,3] Nerve blocks have been previously studied as a method to control herpes zoster pain in outpatient pain clinics and inpatient settings. This study aims to investigate whether emergency department ultrasound guided nerve blocks can prevent PHN and effectively treat acute herpes zoster pain.

II. Background and Significance

Varicella-zoster virus causes acute herpes zoster, which causes characteristic burning dermatomal pain that self resolves within two to three days for most patients. Unfortunately for some, the pain can persist for months after initial symptoms.^[4] Pain that persists between one to three months is commonly classified as subacute herpetic neuralgia. Pain that persists three or more months after initial symptoms is classified as postherpetic neuralgia (PHN).^[5] The pain associated with acute herpes zoster is due to hemorrhagic inflammation and fibrosis of the peripheral nerve, dorsal root, and dorsal root ganglion, but the mechanism of PHN is not well understood. It is hypothesized that the afferent neuron activity triggered by tissue damage causes changes in dorsal nerve roots leading to hypersensitivity and eventually spontaneous activity and ectopic discharges from the inured nerves and dorsal roots regardless of tissue insult. ^[6,7,8]

Over 200,000 cases of herpes zoster are managed in the emergency room every year in the United States and up to 43% of these patients may develop PHN.^[2,3, 14] Of all patients with acute herpes zoster, 10% will require 3 or more follow-up visits for pain management causing significant burden on the medical system.^[9] Herpes zoster pain can be chronic and intractable, and can significantly decrease a patient's perceived quality of life which in some cases can lead to depression and even suicide.^[10] Commonly, the initial presentation occurs in the emergency department; thus, it is paramount for an emergency room physician to adequately manage the acute pain of herpes zoster. However, herpes zoster pain can be difficult to control. In addition, it is unknown if any treatment modality can minimize the risk of PHN. Current treatment modalities including antivirals, anticonvulsants, oral corticosteroids, and opioids have not shown to be prevent postherpetic neuralgia.^[11]

In outpatient pain clinics and inpatient settings, ultrasound guided nerve blocks using local anesthetics and corticosteroids have been shown to effectively treat acute herpes zoster pain. Several studies have found that patients who received nerve blocks for acute herpes zoster had a reduced incidence of PHN at 3 months.^[12-16] Local anesthetics reduce afferent neuron activity preventing dorsal root automaticity while steroids decrease vasogenic edema reducing tissue damage.^[14] Ultrasound guided nerve blocks have become a widespread method of pain management in the emergency department for various clinical scenarios. The purpose of this study is to investigate the efficacy of utilizing ultrasound guided nerve blocks in preventing PHN in the emergency department and managing acute herpes zoster pain.

III. Study Objectives

The goal of this study is to evaluate the rate of PHN development in emergency department patients who receive ultrasound guided nerve blocks using bupivacaine and dexamethasone for acute herpes zoster. We will also study the effectiveness of the block in managing acute herpes zoster pain. The primary outcome is the percentage of patients who have significant herpetic pain at 1 month and 3 months after receiving the nerve block. Secondary outcomes measured are pain scores at 1 hour, 1 month, and 3 months post-nerve block. The amount of opioids used after discharge as well as the number of return visits for herpetic pain will also be recorded.

IV. Hypothesis

Our hypothesis is that patients who receive nerve blocks will decrease the occurrence of PHN development at 1 month and 3 months post-treatment. Our secondary hypothesis is that nerve blocks will decrease pain scores at 1 hour, 1 month, 3 months, as well as reduce the amount of opioids used and number of return visits for herpetic pain.

V. Study Design

This study will be a single center prospective observational study that will be conducted in the emergency department of an urban hospital center. A trained emergency medicine physician will screen and assess the patient for eligibility. Once the patient is determined to be eligible, informed consent will be obtained. A trained EM physician will then administer a nerve block using bupivacaine and dexamethasone to a patient with acute herpes zoster. The patient will be started on Acyclovir 800 mg five times daily for seven days. For mild to moderate breakthrough pain, the patient will be prescribed a 5-day course of Tylenol 650 mg and Ibuprofen 400 mg taken up to every 8 hours together. For severe breakthrough pain, the patients will be prescribed a two-day course of 7.5 mg morphine sulfate immediate release to be taken up to every 6 hours. The location of the nerve block and dosage of injected medications will depend on the distribution of the affected dermatome. The dermatomal distributions with their associated nerve blocks and medication dosages are shown the table below.

Herpes Zoster Distribution	Nerve Block Type	Medication
T2-T9	Serratus Plane	30 mL 0.25% bupivacaine and 8
		mg Dexamethasone
C2-C3	Greater Occipital Nerve	2 mL 0.25% bupivacaine and 4
		mg dexamethasone
C3-C4	Superficial Cervical Plexus	10 mL 0.25% bupivacaine and 4
		mg dexamethasone
Anterior Abdominal Wall T6 – L1	Transversus Abdominis Plane	30 mL 0.25% bupivacaine and 8
		mg dexamethasone

A numerical verbal rating scale will be used to assess the patient's pain pre-injection and at 1-hour post nerve block. We will then call the patient at the 1 week, 1 month, and 3-month

post-nerve block time intervals to assess the patients' pain. We will also record the number of follow-up visits for herpetic pain and the amount of additional pain medications used.

When called the patient will be asked a series of questions:

- 1. Do you continue to have pain associated with your herpes zoster infection?
- 2. If so, how would you rate your pain from a scale of 0-10? 10 being the worst pain you have ever had in your life.
- 3. About how much pain medication have you been using since the initial nerve block? How many doses of Ibuprofen or Tylenol per day for how many days? How many doses of morphine sulfate immediate release or other opioids were taken per day for how many days?
- 4. If you used other forms of pain controllers, what were they and how often and for how long did you use them?
- 5. Have you seen your primary care doctor, pain clinic, emergency department, or other pain management follow-up visits for management of your herpes pain? If so, how many visits have you made?
- 6. What side effects have you had since the nerve block?

1. Subjects:

The study population is Maimonides Medical Center emergency department patients older than 18 years of age presenting with acute herpes zoster patient with characteristic dermatomal vesicular skin lesions within 30 days of initial symptoms.

2. Eligibility Criteria:

The inclusion criteria are patient age over 18 with herpes zoster pain onset within 30 days of characteristic dermatomal herpes zoster rash. The exclusion criteria are allergy to bupivacaine, signs of infection over herpes zoster site, greater than 30 days duration of pain, pain across more than one dermatome and pregnant and/or breastfeeding women.

3. Design:

The primary outcome is the percentage of patients who have significant herpetic pain at 1 month and 3 months after receiving the nerve block. Secondary outcomes measured are pain scores pre-injection, and 1 hour, 1 month, and 3 months post-nerve block. The number of tablets of opioids and other analgesics used after discharge as well as the number of return visits for herpetic pain will also be recorded.

4. Data Collection Procedures:

The numerical verbal rating scale pain score will be recorded by a research staff member at 1 hour after administration of nerve block. The patients will then be called at 1 week, 1 month, and 3 months post nerve block for assessment of NRS as well as number of follow-up visits and amount of analgesics used. A medication track form/log will be given to the patients to help record the amount of medications taken in the first week. The patients will be stratified by age: those under 50, 50-59, 60-69, and 70 and older as well as herpes zoster vaccination status.

5. Sample Size:

Earlier studies show the incidence of post herpetic neuralgia to be up to 43% in patients who are diagnosed with acute herpes zoster.^[14] We will calculate a sample size required to achieve an α of 5 and power of 80% to detect a clinically relevant reduction in the incidence of PHN from 43% to 10%. We will allow for 10% loss of follow-up.

6. Expected Outcomes:

We expect that patients undergoing ultrasound guided nerve block will have decreased incidence of subacute herpetic neuralgia and PHN. We also expect pain to be well controlled at 1 hour, 1 week, 1 month, and 3 months post nerve block.

7. Adverse Event Reporting:

Side effects of local anesthetics are rare but usually target the central nervous system (numbness, metallic taste, anxiety, visual changes, muscle twitching, seizure, somnolence, coma, respiratory depression) and the cardiovascular system (hypertension or hypotension, tachycardia or bradycardia, ventricular arrhythmias and/or asystole). All adverse and unexpected events will be recorded during the calls in the 3-month follow-up period and reported to the IRB as per hospital policy. Adverse events will also be included in the final publication.

References

- 1. Kim M. O'Connor and Douglas S. Pauw. Herpes Zoster. Medical Clinics of North America. July 1, 2013. 97(4); 503-522.
- 3. Kosuke Kawai, Berhanu G Gebremeskel, Camilo J Acosta. Systematic review of incidence and complications of herpes zoster: towards a global perspective. BMJ Open. 2014 June.
- 4. [name]., and [name]. Postherpetic Neuralgia pathogenesis, Treatment, and Prevention. N Engl J Med. 1996. 333:32-42.
- 5. Robert W. Johnson, Robert H Dworkin. Treatment of herpes zoster and postherpetic neuralgia. BMJ. 2003; 326:748.

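### Section V.7 promises to record all adverse and unexpected events at the calls, but the call script asks only about side effects and herpes-pain visits, so other events are not systematically asked about

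*Protocol*

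**What the plan says.** Section V.7 (Adverse Event Reporting) sets the target: "All adverse and unexpected events will be recorded during the calls in the 3-month follow-up period". It adds that these events go to the IRB under hospital policy and that adverse events will appear in the final publication. The telephone calls are the only route of collection that V.7 names.

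Section V (Study Design) gives the content of those calls. It introduces the script with "When called the patient will be asked a series of questions" and lists six numbered questions:

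- Questions 1 to 4 deal with pain and with the analgesics or other pain treatments used.
- Question 5 asks about visits to the primary care doctor, pain clinic, emergency department, "or other pain management follow-up visits for management of your herpes pain".
- Question 6 is the safety question: "What side effects have you had since the nerve block".

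Section V.4 (Data Collection Procedures) gives the timing, "The patients will then be called at 1 week, 1 month, and 3 months post nerve block", and the purpose, "for assessment of NRS as well as number of follow-up visits and amount of analgesics used". Adverse events are not in that list. The only record kept by the patient is a medication log for the first week.

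**The concern.** The script covers less than V.7 promises. Asking for side effects invites the patient to decide first whether a treatment caused the problem and to report only what passes that test. V.7 has no such condition: it covers all events and names unexpected ones in particular, which a patient may well not recognise as an effect of treatment.

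At stake is the completeness of the safety data. If callers keep to the script, the adverse events sent to the IRB and published would consist mainly of what patients themselves consider side effects. A reader who takes V.7 at its word would understand them as all events over three months. No later analysis can recover events that nobody asked about.

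**Working it through.** No arithmetic applies. The protocol states no event rate and no final sample size, and the point depends on neither. The check is to set the promise beside each instrument that could deliver it.

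| Source | What it covers | Would it prompt for a health problem the patient does not see as a side effect? |
|---|---|---|
| V.7 | All adverse and unexpected events over 3 months | This is the target |
| Questions 1 and 2 | Presence and severity of zoster pain | No |
| Questions 3 and 4 | Analgesics and other pain treatments | No |
| Question 5 | Visits made for herpes pain | No |
| Question 6 | Side effects since the block | Not directly; only if volunteered or probed |
| V.4, purpose of the calls | Pain score, visits, analgesics | No; adverse events not listed |
| V.4, patient log | Medications in the first week | No |

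**Step 1: the wording of Question 6.** The question is open-ended and tied to time. It asks what has happened *since* the block, not what came *from* it. Patients may also take acyclovir, acetaminophen, ibuprofen and morphine under section V, and an effect blamed on any of these is a valid answer. The filter is therefore attribution to some treatment, not to the block alone.

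**Step 2: a case that tests the script.** Suppose a patient goes to an emergency department with a seizure, an event on V.7's own list, and puts it down to another illness. Questions 1 to 4 do not touch it. Question 5 does not, because the visit was not for herpes pain. Question 6 does not prompt for it, because the patient does not think of it as a side effect. The event is recorded only if the patient mentions it unasked or the caller goes beyond the script.

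**Step 3: other routes.** None of the remaining instruments closes the gap. The log covers medication only and stops after the first week. V.4 does not tell call staff that collecting adverse events is one of their tasks.

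**Count.** Of six questions, one concerns safety and asks for side effects, and one concerns health-care use and is limited to herpes pain. None asks in neutral terms about a new illness, symptom, visit or admission.

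**The case against.** The strongest reply is that V.7 itself obliges staff to record every adverse and unexpected event at the calls, that Question 6 is open-ended, and that section V does not say the six questions are the only ones allowed. An event that is volunteered or probed for can therefore be recorded under the protocol as written. This stands, and it rules out the claim that such events are never elicited. It does not remove the mismatch: a duty to record what comes up does not tell the caller to ask about what the script leaves out.

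A second reply is that V.7 uses its terms loosely. It opens with side effects of local anesthetics and moves to adverse and unexpected events in the same paragraph, so Question 6 may be meant to cover both. That is possible, but the patient hears only Question 6, and its term is narrower in ordinary use.

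A third reply is that Question 5 is no faulty safety question. This is right. It measures return visits for herpetic pain, a recorded outcome, and its restriction suits that purpose. It matters here only because no other question asks about visits.

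A reader might also infer that patients who have died or are in hospital when called disappear into the loss allowance with no event recorded. The documents do not say so. The sentence "We will allow for 10% loss of follow-up" in V.5 is a sample-size allowance, not a rule for classifying safety data, and a call that finds a patient dead or admitted has revealed an event that V.7 requires to be recorded. For the same reason 10% should not be used as the size of the problem. A worst case in which every lost patient had an event applies to any study with that loss and would not change if Question 6 were reworded.

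**Conclusion.** The point holds as a mismatch between V.7 and the call script. Events that the patient does not regard as a side effect of some treatment are not systematically asked about, so the reported adverse events may be too few. Among patients reached, events missed in this way can only lower the count. How many would be missed cannot be estimated from the documents, and no figure should be attached.

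The conclusion assumes that callers broadly follow the printed script and that no other collection form exists beyond what the protocol describes. If staff already probe for any health problem, the gap is one of documentation only.

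The scope is limited to the completeness of safety reporting; the primary outcome, the pain scores and the sample size are untouched. It still merits a change, because the question as printed falls short of the protocol's own commitment and a better one costs almost nothing.

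**What to change.** 1. Replace Question 6 with a neutral question, for example: *Since the nerve block (or since our last call), have you had any new or worse health problem, emergency visit or hospital admission for any reason?* The study physician, not the patient, then judges whether the event is related to treatment.
2. Add adverse events to the purposes of the calls in V.4, so that V.4, V.7 and the script agree.
3. Leave Question 5 unchanged, because it measures the return-visit outcome.

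The cost is one reworded question and a few words in V.4. The small downside is that more unrelated events will have to be listed and assessed.

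A check of hospital records for patients who cannot be reached is a separate, optional addition; this mismatch does not require it.

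### PHN is defined from first symptoms, but the primary outcome is timed from a block given up to 30 days later, so the calls do not measure PHN on the protocol's own clock

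*Protocol*

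**What the plan says.** **Definition.** Section II (Background and Significance) says: "Pain that persists three or more months after initial symptoms is classified as postherpetic neuralgia (PHN". The Introduction uses the same time origin with a slightly stricter limit: "debilitating pain that persists more than three months after the initial symptoms". Section II also gives the earlier stage its own name: "Pain that persists between one to three months is commonly classified as subacute herpetic neuralgia".

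**Outcome.** Sections III and V.3 count from the block: "The primary outcome is the percentage of patients who have significant herpetic pain at 1 month and 3 months after receiving the nerve block". The follow-up calls in V and V.4 (1 week, 1 month, 3 months) also run from the block. The Hypothesis says that blocks "will decrease the occurrence of PHN development at 1 month and 3 months post-treatment".

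**Delay from onset to block.** V.1 describes patients with "characteristic dermatomal vesicular skin lesions within 30 days of initial symptoms", and V.2 excludes anyone with more than 30 days of pain. The V.2 inclusion criterion, "herpes zoster pain onset within 30 days of characteristic dermatomal herpes zoster rash", relates pain to rash. It does not itself limit the time from onset to block; the exclusion does.

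**Reference.** V.5 takes an incidence of up to 43% in diagnosed acute zoster and plans to detect a fall to 10%. It does not say from what point that incidence is counted.

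**The concern.** The stated goal is the rate of PHN, and the planned sample size rests on PHN incidence. Yet no assessment is tied to the event from which the protocol counts PHN. Three things follow.

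- Patients reach each call at different times since onset, with a spread of up to 30 days.
- A patient whose pain lasted beyond three months from onset but ended before the 3-month call has PHN by Section II and is recorded as pain-free. The call questions ask whether pain continues, not when it stopped, so this patient cannot be identified later.
- The 1-month result is called PHN in the Hypothesis, although no patient can meet the definition at that call.

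At stake is whether the reported percentage is the PHN rate the protocol says it studies, and whether it can be set beside 43%.

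**Working it through.** **Step 1: time since onset at each call.** Inputs: calls at 1 and 3 months after the block (V.4); delay from onset to block of 0 to 30 days (V.1 and the exclusion in V.2), taking first symptoms as the onset of pain. With 30.4 days to a month:

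| Delay (days) | 1-month call, months since onset | 3-month call, months since onset |
|---|---|---|
| 0 | 1.00 | 3.00 |
| 7 | 1.23 | 3.23 |
| 14 | 1.46 | 3.46 |
| 30 | 1.99 | 3.99 |

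**Step 2: compare with the definitions.** The 1-month call always lies inside the one-to-three-month band that Section II calls subacute. At the 3-month call, anyone still in pain has had it for at least three months, so the timing creates no false PHN. It loses only patients whose pain stopped between month 3 and the call. The error is therefore zero or a loss, never a gain.

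**Step 3: how large the loss could be.** The protocol gives no resolution rate after month 3, so this is illustration only. Assume that 43% is the rate at exactly 3 months from onset and that a share q of those in pain at month 3 recovers per further month. For a delay of d days, observed rate = 43% × (1 − q)^(d/30.4).

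| q per month (assumed) | d = 7 | d = 30 | d spread evenly over 0–30 |
|---|---|---|---|
| 0% | 43.0% | 43.0% | 43.0% |
| 10% | 42.0% | 38.8% | 40.8% |
| 20% | 40.8% | 34.5% | 38.6% |
| 30% | 39.6% | 30.2% | 36.2% |

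If nobody recovers in the gap, the loss is nil. For q of 10% to 30% it is about 2 to 7 points with evenly spread delays (43.0 − 40.8 = 2.2; 43.0 − 36.2 = 6.8). It is about 4 to 13 points if every patient is blocked on day 30 (43.0 − 38.8 = 4.2; 43.0 − 30.2 = 12.8).

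**Step 4: a force in the other direction.** The Introduction says most zoster pain resolves within a week. Patients who come for a block days or weeks after onset are still in pain and may be the more persistent cases. Assume that a share s of all diagnosed cases is pain-free before they could be enrolled and that none of these go on to PHN. The month-3 rate among enrolled patients is then 43%/(1 − s), and at a 30-day delay the observed rate is 43%/(1 − s) × (1 − q)^(30/30.4):

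- s = 10%, q = 10%: 43.1%
- s = 20%, q = 20%: 43.1%
- s = 10%, q = 30%: 33.6%
- s = 30%, q = 10%: 55.4%

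Against 43%, the net result can be lower, equal or higher.

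**The case against.** Counting outcomes from treatment is a legitimate choice, and pain at a fixed time after the block is clear as to timing. An onset clock would leave only 2 to 3 months of follow-up after the block, which exchanges one source of variation for another. The 43% comes from a source that the reference list titles a meta-analysis of nerve blocks for preventing PHN. If that source counts from treatment, the protocol's timing already matches its comparator. Delays may also be short, since Section II says first presentation is commonly in the emergency department. Finally, V.2 obliges screening to establish how long pain has lasted, so the case report form may hold onset even though V.4 does not list it.

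Most of this stands, and it is why the post-block outcome should be kept. It does not remove the mismatch with the protocol's own definition, or the PHN label at 1 month.

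A reader might go further and infer that looking late biases the observed rate downward and so favours the hypothesis, or might attach a false-positive rate to it. The documents do not support either. The loss may be zero, the time origin of the 43% is not stated, and selection of patients still in pain may act the other way. It is true that Section II applies the 43% to emergency department cases, so the protocol treats the reference as matching its population, but that does not settle the time origin. A false-positive rate would also need a sample size and a test, and V.5 states neither.

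**Conclusion.** The mismatch is confirmed from the text: two time origins that differ by up to 30 days and are nowhere reconciled. Two consequences are firm. At the 3-month call, timing can only miss cases that meet the protocol's definition. At the 1-month call, the outcome is pain in the subacute range, not PHN; V.6 itself lists the two conditions separately.

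The number of missed cases is not determinable from the documents. The ranges in the working rest on assumed resolution rates, on assumed delays and on reading 43% as a rate at 3 months from onset. The net direction against the 43% is undetermined. This is a cheap improvement in measurement and labelling, not evidence that the result would lean one way.

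**What to change.** 1. Record the dates of first symptom and of the block for every patient, and list both in V.4.
2. Add one question to each call: if the pain has stopped, the date on which it stopped.
3. Keep the post-block outcome in V.3. Beside it, report the PHN rate classified from symptom onset under the Section II definition, with the distribution of the onset-to-block interval.
4. Label the 1-month result as subacute herpetic neuralgia or herpetic pain, not PHN, and reword the Hypothesis to match.
5. State in V.5 which time origin the 43% uses, so that it is compared with the result on the same clock.

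Cost: two date fields, one question and a few sentences, with no extra calls or patients. The stop date carries some recall error. For the PHN classification this matters only around the 3-month mark from onset, which lies at most 30 days before the 3-month call. The stop date also does not show how severe the pain was at month 3, so it cannot by itself establish that pain was significant then. That is a further reason to report this rate beside the post-block outcome and not in its place.

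### A single treated group with no comparator is planned around a fall in PHN from 43%, a rate the protocol words as a maximum and gives for PHN only

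*Protocol*

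**What the plan says.** - **Design (Protocol, section V).** "This study will be a single center prospective observational study". The only treatment path is the block: "A trained EM physician will then administer a nerve block using bupivacaine and dexamethasone to a patient with acute herpes zoster". Sections V to V.6 describe no untreated, usual-care or named historical group. V.4 stratifies by age and vaccination status only.
- **Goal (section III).** Descriptive: the rate of PHN among emergency department patients given the block.
- **Primary outcome (sections III and V.3).** "The primary outcome is the percentage of patients who have significant herpetic pain at 1 month and 3 months after receiving the nerve block".
- **Hypothesis (section IV).** "patients who receive nerve blocks will decrease the occurrence of PHN development at 1 month and 3 months post-treatment".
- **Expectation (section V.6).** "We expect that patients undergoing ultrasound guided nerve block will have decreased incidence of subacute herpetic neuralgia and PHN".
- **Sample size (section V.5).** "Earlier studies show the incidence of post herpetic neuralgia to be up to 43% in patients who are diagnosed with acute herpes zoster". The next sentence begins "We will calculate a sample size required to achieve" and sets the aim to "detect a clinically relevant reduction in the incidence of PHN from 43% to 10" per cent, with alpha 5 (read as 5%), power 80% and 10% loss to follow-up. No N is given. Section II also words the 43% as a maximum.
- **Definitions (section II).** Pain lasting one to three months is subacute herpetic neuralgia. Pain lasting three months or more after the first symptoms is PHN.

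**The concern.** A decrease needs something to decrease from. With one treated group, the only candidate in the protocol is the 43%, and it fits that role badly in two ways.

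1. It is introduced as an upper limit and then used, one sentence later, as the starting rate.
2. It is a rate for PHN, so by section II it concerns three months or later. It gives no reference for pain at 1 month, which is half of the primary outcome. Section IV's mention of PHN at 1 month does not fit the protocol's own definition.

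The stake is a claim of prevention. Sections I and II say that most zoster pain resolves by itself early on, so a low rate after the block does not by itself show that the block worked. If the observed rate is set against 43% and the cohort's rate without the block is lower, natural resolution can be read as a treatment effect. Without a concurrent control or a justified reference, the data cannot separate the two.

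**Working it through.** **No stated figure to reproduce.** V.5 gives inputs but no N. The check therefore takes those inputs under the single-arm reading, which matches the one group described.

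**Inputs from V.5:** reference p0 = 0.43, target 0.10, alpha 5%, power 80%.

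**Assumptions:** exact binomial test with a lower tail of 2.5% (V.5 does not state sidedness); significant pain at 3 months counted as PHN; true rates other than 43% chosen for illustration.

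**Step 1: rule and size.** A reduction is declared if X ≤ c, where c is the largest value with P(X ≤ c | n, p0) ≤ 0.025, and P(X ≤ c) = Σ C(n,k) p^k (1−p)^(n−k) over k = 0 to c.

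- At n=14 and p=0.43, the terms for k = 0, 1, 2 are 0.0004 + 0.0040 + 0.0198 = 0.0242. Adding k = 3 gives 0.0839, so c = 2.
- At p=0.10, the same terms are 0.2288 + 0.3559 + 0.2570 = 0.8416.
- At n=13, c drops to 1 and power at 10% is 0.62. So n=14 is the smallest size with at least 80% power (14/0.9 = 15.6, so 16 after 10% loss).

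**Step 2: a block with no effect.** With n=14 and c=2, the chance of declaring a reduction against 43% is:

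| True rate without the block | P(X ≤ 2) |
|---|---|
| 50% | 0.7% |
| 43% | 2.4% |
| 35% | 8.4% |
| 30% | 16.1% |
| 25% | 28.1% |

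**Step 3: power at a true 10% if the reference is lower.** At n=14, c is reset so that the tail stays within 2.5%:

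| Reference | c | Power at 10% | Smallest n with 80% power |
|---|---|---|---|
| 43% | 2 | 84% | 14 |
| 35% | 1 | 58% | 22 |
| 30% | 0 | 23% | 31 |

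**Step 4: which side of 43% might the cohort lie on?** The documents do not give its rate without the block, and two features pull in opposite directions.

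- V.2 admits patients with pain for up to 30 days. Those still in pain weeks after onset may be more likely to stay in pain, which would raise the rate.
- Section V times the 3-month call from the block, while section II times PHN from the first symptoms. The call may come up to about four months after onset, which leaves more time for resolution and would lower the rate.

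**The case against.** The strongest reply is that the study calls itself observational, has a descriptive goal, and already has a plain percentage as its primary outcome. A hypothesis and an expectation are not conclusions. The 43% is only a planning input, and a single-arm study against a historical rate is a legitimate design.

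Much of this stands. The hypothesis may stay, and a declared benchmark would be acceptable. Planning on one time point is also ordinary practice, and section IV's wording about 1 month may be loose phrasing, since V.6 names the two conditions separately. What remains is that the protocol neither declares 43% as a historical benchmark nor justifies it, and that it uses a maximum as the starting point for an expected decrease.

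A reader might infer more than the documents support:

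- **That the result will be tested against 43%.** The protocol does not say so. This is inferred from IV and V.5.
- **That 43% is too high, so the study is biased towards success.** Only the shift from a maximum to a starting rate is documented. The cited source is not at hand, and the cohort's rate could lie above 43%, which would make the comparison strict.
- **That the missing N, test, decision rule or threshold for significant pain is a fault.** These may stand in the SAP, which is not shown, and are no part of this point.

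**Conclusion.** The point holds in limited form and should be fixed. The protocol describes one treated group without a comparator, expects a decrease, and plans from a rate that it words as a maximum and gives for PHN only.

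Under the single-arm reading with n=14, a nominal 2.4% chance of crediting an ineffective block becomes 8.4% at a true rate of 35%, 16.1% at 30% and 28.1% at 25%. These figures rest on an assumed use of 43% as the benchmark, an assumed exact test, and assumed true rates. They show how sensitive the conclusion is to the reference rate. They do not show that an error will occur. Confidence is medium.

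**What to change.** **Change**

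- In IV, V.5 and V.6, state that the study is single-arm and has no control.
- Report the proportions with significant pain at 1 month and at 3 months, each with an exact 95% confidence interval, as the primary result. This matches the goal in section III.
- Call the 1-month outcome subacute herpetic neuralgia, not PHN, in line with section II.
- If a historical comparison is kept, replace the maximum with a justified typical rate for the same endpoint, the same time point and a comparable population. Restate the power against it, show the conclusion over a range of reference rates, and do not rest a claim of prevention on it alone.

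**Cost**

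Protocol wording and a rewritten sample-size paragraph, with no new visits or data items. The claim becomes weaker, and the stated power becomes less favourable if the justified rate is below 43%. Restating the power is enough. More patients are needed only if 80% is to be kept against a lower reference: about 22 at 35% or 31 at 30%, against 14 at 43%, all before loss to follow-up.
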